5. BIAS CONTROL

This is a large trial, randomised with permuted blocks (by centre and ICU). Anaesthetists, surgeons, and intensivists will have knowledge of Group identity. Similarly, it is expected that other surgical and nursing staff, and research staff conducting the in-hospital daily reviews, cannot be properly blinded to Group identity. But research staff conducting Day 3, 1-12 mth follow-ups MUST be blinded to Group allocation. Secondary outcomes are clearly defined in the protocol; disputes will be resolved by blinded assessors (endpoint adjudication committee).

6. SAMPLE SIZE AND STATISTICAL ANALYSIS

All statistical analysis will be overseen by [name], Monash University Department of Epidemiology and Preventive Medicine. The intention-to-treat population will include all patients randomly assigned to groups AND undergoing induction of anaesthesia.

Our initial sample size calculation was based primarily on our own data and other published studies. Our ENIGMA-II trial (n>5000 enrolled to date), with a lower risk study population, has a disability-free survival rate of 70% (15% mortality, 15% new disability) at 1 year after surgery). The most recent large data comes from the UK, where the 1-year mortality for open colorectal surgery was 17% in the 31,847 patients with pre-existing comorbidity (84). Reductions in serious complication rates have exceeded 25% in pooled analyses of similar studies(3, 82), and pre-existing major comorbidity increases mortality risk up to 16-fold (83). Using a type I error of 0.05 and survival analysis, with an expected one year disability-free survival probability of 65% (65) and a hazard ratio of ≥1.25, 1300 patients in each group will provide 90% power. Target recruitment was set at 2800 patients to account for losses due to follow-up. The Trial Steering Committee met on the 30th June, 2016, to discuss the results of a data quality committee review and statistician's report of the accruing incidence of disability. With near-complete information on 2,578 enrolled patients there were 300 events (disability or death); that is, a 12-month event rate of 14.6% - this is lower than expected. An increase in the trial sample size to 3,000 (≈380 events), which provides 80% power to detect HR≤0.75. This protocol amendment was accepted by the Steering Committee.

Analyses will be intention-to-treat. For analysis of the composite death-disability endpoint, we will use the Cox proportional hazards regression model with treatment as the only covariate to produce an unadjusted hazard ratio with a 95% confidence interval, together with Kaplan-Meier survival curves for graphical display; Analysis of secondary outcomes measured on a binary scale will be performed using log-binomial regression to estimate risk ratios with 95% confidence intervals, or exact logistic regression to approximate risk ratios if the number of events in either arm is fewer than 10. Time to event outcomes will use Cox proportional hazards regression as above. For analysis of the primary composite death-disability endpoint we will use the Cox proportional hazards regression model with treatment as the only covariate to produce an unadjusted hazard ratio with a 95% confidence interval, together with Kaplan-Meier survival curves for graphical display.

Outcomes measured on a continuous scale with a right skewed distribution will be log transformed and analysed using linear regression with robust standard errors, and outcomes with a left skewed distribution will be analysed with median regression with standard errors estimated using 1000 bootstrap replications.

Sensitivity Analysis

Sensitivity analyses for all outcomes will use regression models with additional adjustment for the stratification variables of site and planned HDU/ICU destination status, plus any variables exhibiting substantial imbalance across treatment arms at baseline.

Sensitivity to missing outcome data will be performed using multiple imputation if the proportion of missing outcome data is greater than 5%. This will use baseline and auxiliary post-baseline information to inform the imputations under a *missing at random* assumption.

Planned sub-group analyses will assess patient sex, age groups (approximate quintiles), country, bowel surgery (yes/no), and use of any goal-directed techniques (yes/no). The latter include invasive or non-invasive cardiac output, stroke volume or pulse pressure variation, and oesophageal Doppler; but not include CVP monitoring. For these we will undertake tests for interaction by adding treatment-by-covariate terms to the regression models.

Additional prespecified subgroups will be tested for heterogeneity of effect, and their results considered exploratory (only): country, body mass index (BMI) categories (underweight, normal, overweight, obese, ≥super obese), ASA physical status (1/2, 3, 4), planned HDU/ICU destination status, and duration of surgery (approximate quintiles).

7. INTERIM ANALYSIS

Interim analyses will consider the defined study endpoints, but include a specific consideration of 90-day mortality (because the primary endpoint is not finalised until 1 year after study entry) after enrolment of 1,445 patients, using the boundaries of O'Brien and Fleming. Results will be made available to the Data and Safety Monitoring Committee.

8. SECONDARY ANALYSIS

We plan several substudies (to be funded from other sources), each of which will have a separate protocol and authorship plan (using an expanded list of contributors). Additional blood tests and other investigations will be done at selected hospitals according to local interest and expertise.

- 8.1 Cost-effectiveness, to include hospital stay and complications as we have done previously (85)
- **8.2** Hyperchloraemic acidosis (to measure strong ion difference, Cl-, lactate, albumin)
- **8.3** Pulmonary oedema (to measure FiO2/PaO2 ratio, CT/CXR-confirmed atelectasis)
- 8.4 Coagulopathy (to measure blood loss, platelet count, fibrinogen, INR, APTT, Hb flux, transfusion)
- **8.5** Sepsis (to measure fever, WCC, CRP and possibly other biomarkers)
- 8.6 AKI and hepatic injury
- 8.7 Postoperative cognitive deficit
- 8.8 Feeding and return of bowel function
- 8.9 Wound healing and anastomotic leak

9. PERSONNEL RESPONSIBILITIES

9.1 Investigators

The Steering Committee will consist of the principal investigator ([name] [Chair]), and other clinician-researchers in anaesthesia, surgery and intensive care medicine, plus the trial statistician – see below.

Each site investigator must ensure that all staff conducting the study are qualified to do so.

Each site investigator must submit the study protocol to the Ethics Committee or equivalent regulatory body and obtain approval prior to commencing the study.

Each site investigator must ensure that all staff involved with the study are fully instructed on the study procedures and are given access to the study protocol and other information relating to the study.

Each site investigator must ensure that the study is conducted in accordance with this protocol, ICH GCP notes for Guidance on Good Clinical Practice (CPMP/ICH/135/95) and in Australia with the NHMRC National Statement on Ethical Conduct in Research Involving Humans.

It is each site investigator's responsibility to ensure that written, informed consent is obtained from each patient prior to entering the study.

Each site investigator must ensure that the web-based CRFs are complete and accurate on completion of the study. Each site investigator will ensure that the quality control procedures are performed on both the CRFs and the data base.

It is the principal investigator's responsibility, in conjunction with the chief investigators, to write the Study Report at the completion of the study. Authorship guidelines are described in Section 11.

9.2 Monitor

Not applicable.

9.3 Sponsor

Alfred Health, as an investigator initiated study.

9.5 Endpoint Adjudication Committee (EAC)

Confirmation reports of all detected outcomes will be de-identified and re-labelled with study number. The committee will consist of experienced perioperative physicians. Details are provided in the Procedures Manual. Their role will be to resolve any uncertainty as to any of the above outcomes: additional advice can be sought by consultation with subspecialists.

10. DATA SAFETY MONITORING COMMITTEE

The committee consists of [name] (Chair, *intensivist*, Smiths Medical Professor of Anaesthesia & Critical Care, University College London (UK); Co-Director, Surgical Outcomes Research Centre), [name] (*surgeon*, Professor of Surgery and Public Health, The Alfred & Monash University Director, National Trauma Research Institute; Melbourne), [name] (*epidemiologist and triallist*, Professor of Epidemiology and Preventive Medicine; Head, School of Applied Clinical and Public Health Sciences; Monash University), [name] (*anaesthetist*, Professor of Anaesthesia, Flinders University), and [name] (*independent statistician*, MCRI).

The DMSC will discuss the interim results and vote for continuation or stopping the trial. A majority vote to stop the trial will be communicated to the Steering Committee at the Trial Coordinating Centre according to predetermined stopping rules (as above) and consideration of other relevant evidence. Their conduct is to be guided by the paper by DeMets et al. (86). Further details are provided in the DSMC charter.

11. ADMINISTRATIVE PROCEDURES

11.1 Amendments to the Protocol

All modifications of the study will be written and filed as amendments to this protocol, maintaining original section identification. Such modification(s) will be made by the principal investigator, with endorsement by the Steering Committee and with the approval of the Ethics Committee (where applicable).

Any modifications to the study will be applied for all subsequent patients

11.2 Early Termination or Extension of the Study

The investigator (with Ethics Committee approval) may discontinue or extend the study at any time.

11.3 Confidentiality/Publication of Study Results

Interim and preliminary results should not be discussed or presented outside the Trial Group, unless authorised by the chair of the Trial Steering Committee. The investigators plan to publish the results in a peer-reviewed journal.

11.4 Retention of Records

All CRFs and all other documents associated with this study must be archived for at least 7 years following the completion of the trial, in accordance with TGA requirements.

11.5 Audits

For the purpose of compliance with ICH GCP notes for Guidance on Good Clinical Practice (CPMP/ICH/135/95), it may be necessary for a regulatory agency to conduct a site audit.

Random audits may be conducted throughout the trial at the discretion of the Trial Steering Committee.

12. ETHICAL PROCEDURES

12.1 Guidelines for Good Clinical Practice

This study is to be performed in accordance with ICH GCP notes for Guidance on Good Clinical Practice (CPMP/ICH/135/95).

12.2 Precautionary Advice

None specifically required.

12.3 Participant Information Sheet and Consent Form

The investigator or delegate will explain the study verbally to the patient. The patient will then be given a copy of the PI&CF and given an opportunity to read it and ask any questions of the investigator. The patient will be encouraged to obtain additional information about the study from an independent source. Once the patient is satisfied with the information they have received, has had an opportunity to ask questions and obtain additional information, and the investigator is satisfied that the patient truly understands the nature of the study, the patient will be asked to sign the consent form.

The signing of the consent form must take place in front of a witness and that witness must also be satisfied that the patient has a good understanding of the study. Each patient's signed consent form will be retained by the investigator.

Patients will be advised that they are free to refuse to participate in, or to withdraw from the study at any time. The medical care provided will not be affected by agreement or refusal to participate in this study. The original Consent Form for each subject will be stored in the Investigators file and a copy of the consent form will be placed in the patient's medical record.

12.4 Ethics Committee

This protocol will be submitted to the Ethics Committee (or relevant regulatory body) at each site and their approval obtained.

The RELIEF Trial

REstrictive versus LibEral Fluid Therapy in Major Abdominal Surgery

www.relief.org.au

On behalf of the Australian and New Zealand College of Anaesthetists Clinical Trials Network (ANZCA CTN), and the Australian and New Zealand Intensive Care Society Clinical Trials Group (ANZICS CTG)

ClinicalTrials.gov Identifier: NCT01424150

SAP August 29, 2017

Study title: Restrictive versus liberal fluid therapy in major abdominal surgery

Protocol Number: Anaesthesia Research 046

Sponsor: Alfred Health, Melbourne

Funding source: The Australian National Health and Medical Research Council (APP1043755)

RELIEF Statistical Analysis Plan

August 29, 2017

We will apply the intention to treat principle, analysing all participants who are enrolled, randomised and undergo induction of general anaesthesia for eligible surgery. Patients are followed for the duration of the trial, unless they withdraw consent, for which we will use their data up until the time of withdrawal of consent.

ENDPOINT DEFINITIONS

Primary endpoint

The primary end point of the trial is disability-free survival at 1 year after surgery. Disability is defined as a persistent (at least 6 months) impairment in health status, as measured by the 12-item WHODAS score, of at least 24 points when using response scores of 1-5 for each item, reflecting a disability level of at least 25% and being the threshold point between 'disabled' and 'not disabled' as per WHO guidelines. If a single item is missing at an assessment, the mean value of the remaining items will be assigned to the missing item. If more than one item is missing the score will not be calculated for that assessment. With WHODAS assessments being made at (baseline and) 30 days, 3 months, 6 months and 12 months, post-operative disability that persists for at least 6 months is able to be observed to be commencing at the 30 day assessment, the 3 month assessment, or the 6 month assessment. For example, persistent disability commencing at 3 months requires the initial observation of disability (WHODAS >=24) at 3 months which is sustained at each of the 6 and 12 month assessments. Missing WHODAS assessments in patients known to be alive will not be imputed in the primary analysis. Persistent disability observed to commence at the 30 day assessment will be assumed to be related to surgery and will be assigned an onset date of 0.10 days post-surgery. Onset of disability at 3 or 6 months postoperatively will typically be after an incident/illness in the postoperative follow-up period, and for these events the self-reported date of such onset will be utilised. If no such event is documented, then the current time point (interview date) will be used. The time to the primary endpoint is defined as the time of the onset of persistent (>= 6month) disability or death, whichever occurs first. Time at risk will commence at start of surgery to accommodate the potential for intraoperative mortality. Patients not experiencing the primary endpoint event will be censored at their date of last contact. Two supplementary approaches will be utilised to assess sensitivity to handling of missing WHODAS assessments for subjects known to be alive at those assessment times: (a) they will be given a disabled score (WHODAS of 24), and (b) they will be imputed using information from baseline and post-baseline variables (see statistical analysis methods).

Alternative 'new onset disability' definition of the primary endpoint

An additional sensitivity analysis will done for an alternative definition of persistent disability, considered as 'new onset' persistent disability, defined as an increase from baseline of >=4 points in WHODAS scores that persists for at least 6 months. The definition of time to the first of new-onset persistent disability or death will use the same principles as for the primary endpoint.

Secondary endpoints

- 1. Death/survival: all-cause mortality at 90 days, and survival up to 12 months after surgery.
- 2. A composite (pooled) and individual incidence of 30-day mortality and major septic complications, where the latter is defined as the composite of sepsis, surgical site infection, anastomotic leak and pneumonia at 30 days post-surgery. [Detailed clinical definitions are provided in the Protocol]
- 3. Acute Kidney Injury (AKI): according to the Kidney Disease: Improving Global Outcomes group criteria, but not urine output—for Stage 2 or worse AKI defined as at least twofold increase in creatinine, or estimated glomerular filtration rate decrease >50%.

Since a restrictive intravenous fluid regimen may artificially elevate serum creatinine due to a smaller dilutional effect from less intravenous fluids, we will calculate adjusted creatinine following the approach of Liu (2011, Reference 1 below), where

adjusted creatinine = serum creatinine × (1 + cumulative fluid balance/total body water), and assuming that total body water is 60% of body weight, expressed in mL. Serum creatinine is measured on days 1 and 3 and the maximum value in the patient's hospital stay. We will apply adjustments to creatinine levels at days 1 and 3 only. Fluid intake will be accumulated using IV fluids administered intraoperatively, in recovery, and on days 1 to 3 postoperatively, plus the volume of any blood transfusions administered. Fluid outputs from the time of surgery to Day 1 post-surgery will be accumulated using the recorded urine outputs, blood losses and volumes in surgical drains. Missing fluid output components will be imputed to prevent adjustment factors being missing when creatinine levels are present. Fluid outputs on days 2 and 3 are not recorded, so these will be estimated under the assumption of a net fluid balance of zero on each of days 2 and 3; this will form the principal analysis. Sensitivity to this assumption will be assessed using two alternatives: (a) assuming a zero cumulative fluid balance at day 3, and (b) assuming the ratio of intake to outputs up to day 1 persists on days 2 and 3. These two assumptions enclose that of the principal analysis.

We will also report the use of renal replacement therapy up to 90 days after surgery; and delta-creatinine, defined as the difference between the maximum (fluid-adjusted) postoperative serum creatinine level and the preoperative serum creatinine level.

- 4. Pulmonary oedema: documented evidence of respiratory distress or impaired oxygenation and radiological evidence of pulmonary oedema.
- 5. Duration of mechanical ventilation: Defined as additive over all episodes up to 90 days after surgery. This will be reported as (a) the proportion of patients requiring ventilation; and (b) the duration of ventilation in patients receiving ventilation.
- 6. Inflammation: plasma C reactive protein concentration on day 3 after surgery.
- 7. Tissue perfusion marker: peak serum lactate concentration within 24 hours of surgery.
- 8. Any blood transfusion: including red cell, fresh frozen plasma or platelet transfusion, from the initiation of surgery; and quantity of transfusion in patients receiving each product.
- 9. Unplanned admission to HDU/ICU within 30 days of surgery.
- 10. Total HDU/ICU stay in patients admitted to HDU/ICU, including initial admission and readmission duration up to day 30
- 11. Total hospital stay, including any readmission up to day 30.
- 12. Quality of recovery: QoR-15 score on days 1, 3 and 30.
- 13. The rates of serious adverse events, and severity of adverse events (mild, moderate, severe), classified by organ system.

STATISTICAL ANALYSES

Primary endpoint: disability-free survival

Disability free survival will be displayed with Kaplan-Meier plots, and described with event-free proportions in each treatment arm obtained from these plots at days 1, 30, 90, 180 and 365 days post-surgery. Comparison of overall time to events between treatment arms will be made using the log rank test and the Cox proportional hazards model to provide a hazard ratio and 95% CI. Assessment of proportionality of hazards will be based on tests using Schoenfeld residuals. The principal analysis will not impute missing WHODAS measurements for patients known to be alive at those assessment times. The first sensitivity analysis will impute all missing WHODAS assessments for subjects known to be alive at those assessment times by giving them a disabled score (WHODAS of 24). A second sensitivity analysis will impute the missing WHODAS assessments using multiple imputation, with the imputation model employing baseline and post-baseline information predictive of missingness or WHODAS scores, separately in each treatment arm, with results combined across imputations using Rubin's rules.

Alternative 'new onset' definition of the primary endpoint

Analysis of disability-free survival based on the `new onset' persistent disability definition will follow the same approach as for the primary endpoint.

Time to death

Analysis of time to death will follow the same approach as for the primary endpoint.

Other outcomes

Secondary outcomes measured on a binary scale (1, 2, 3, 4, 8, 9) will be summarised using proportions in each treatment arm and analysed using binomial regression with a logarithmic link to estimate Risk Ratios with 95% CIs and p-values, or exact logistic regression to approximate Risk ratios if the number of events in either arm is fewer than 10. Should there be convergence difficulties with log-binomial regression, a log-Poisson model will be employed with robust standard errors.

Duration and length of stay outcomes (5, 10, 11) will be summarised using medians and interquartile ranges, and compared across treatment arms using the Wilcoxon– Breslow– Gehan test, with length of stay in hospital and in intensive care censored at 30 days, and with in-hospital deaths assigned the highest length of stay.

Outcomes measured on a continuous or semi-continuous scale (6, 7, 8, 12) will be summarised by means and standard deviations if reasonably symmetrically distributed and compared between treatment arms using linear regression with robust standard errors. Skewed outcomes will be summarised by medians and interquartile ranges; right skewed outcomes will be log-transformed prior to analysis using linear regression, and left skewed outcomes will be analysed using median regression with robust standard errors.

Additional sensitivity analyses

Sensitivity analyses for all outcomes will use regression models with additional adjustment for the stratification variables of site and planned HDU/ICU destination status, plus any variables exhibiting substantial imbalance across treatment arms at baseline. Sensitivity to missing outcome data will be performed using multiple imputation if the proportion of missing data for the particular outcome is >5%. These analyses will use multiple imputation, employing imputation models with baseline and auxiliary post-baseline variables, and results combined across imputations using Rubin's rule.

Subgroup analyses

Planned subgroup analyses will assess heterogeneity of treatment effects of the primary endpoint across patient sex, age groups (approximate quartiles), country, bowel surgery (yes/no) and intraoperative use of any goal-directed techniques (yes/no). The latter include invasive or non-invasive cardiac output, stroke volume or pulse pressure variation and oesophageal Doppler, but exclude central venous pressure monitoring.

Additional prespecified subgroups will be tested for heterogeneity of effect, and their results considered exploratory: BMI categories (defined as underweight <18.5, normal 18.5-25, overweight 25-30, obese 30-35, super obese >35), ASA physical status (1/2, 3, 4), preoperative planned HDU/ICU destination status, duration of surgery (approximate quartiles), and pre-operative planned use of a goal directed device (excluding CVP monitoring).

Additional analyses of the above subgroups will be performed for the endpoints of newonset disability, composite of 30 day mortality and septic complications, and acute kidney injury.

For these analyses, we will undertake tests for interaction by adding treatment-by-covariate terms to the regression models specified for the main analyses of each outcome.

SAMPLE SIZE RE-ESTIMATION

The original sample size calculation was as follows: Assuming a 12 month disability-free survival probability of 65%, 2650 patients were required to detect a hazard ratio of 0.80 with 90% power using the Freedman method for the sample size for a log rank test. Correspondingly, 850 events were expected to be observed. The sample size was inflated to a total of 2800 patients to account for withdrawals and loss to follow-up.

A sample size reassessment of the assumed primary endpoint event rate was performed after 2578 patients had been randomised. At that time there were 300 primary endpoint events with a 12 month event rate of approximately 15%. Increasing the target sample size to 3000 patients under this same event rate was expected to yield approximately 380 events and afford 80% power to detect a hazard ratio of 0.75.

REFERENCES

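### A WHODAS form with two or more blank items is left unscored even when its answered items already settle which side of 24 the total lies on (minor, cheap to correct)

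*SAP*

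**What the plan says.** The rules are in the SAP under Endpoint definitions, Primary endpoint, and are repeated in part under Statistical analyses.

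- **Scale and cut-off.** Disability is a total of at least 24 on 12 items "when using response scores of 1-5 for each item", described as "reflecting a disability level of at least 25% and being the threshold point between 'disabled' and 'not disabled' as per WHO guidelines".
- **One blank item.** "If a single item is missing at an assessment, the mean value of the remaining items will be assigned to the missing item".
- **Two or more blank items.** "If more than one item is missing the score will not be calculated for that assessment".
- **Persistence.** Disability must last at least 6 months and can start at 30 days, 3 months or 6 months. The worked example is disability first seen at 3 months "which is sustained at each of the 6 and 12 month assessments".
- **Missing assessments, primary analysis.** "Missing WHODAS assessments in patients known to be alive will not be imputed in the primary analysis". "Patients not experiencing the primary endpoint event will be censored at their date of last contact".
- **Sensitivity analyses.** Analysis (a) gives every missing assessment in a living patient a score of 24, which counts as disabled. Analysis (b) uses multiple imputation by arm from baseline and post-baseline information. Neither says that items already answered limit the assigned score.

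Protocol section 3.3.3.1 adds no item-level rule. It refers to the SAP and to a Procedures Manual that is not among the documents.

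**The concern.** The point is about forms that were started and partly answered, not missed visits. The endpoint needs only to know whether the total reaches 24, and a partly answered form can settle that with certainty. The SAP accepts an estimate when one item is blank, but with two blanks it discards a classification that may need no estimate.

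Two consequences follow. In the primary analysis, the event status of some patients would contradict their own recorded answers, and true disability events would be lost. In sensitivity analysis (a), some visits that the answers show to be non-disabled would be called disabled. In (b), an imputed score could fall outside the range that the answers allow. No planned analysis is therefore certain to respect the recorded items. What is at stake is correct classification of a few primary events, not the viability of the trial.

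**Working it through.** **1. The plan's cut-off.** Twelve items scored 1–5 give totals from 12 to 60. (24 − 12)/(60 − 12) = 12/48 = 25%, as the SAP states.

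**2. Bounds.** With k items blank and an answered sum S, the total lies between S + k and S + 5k. The form is provably disabled if S + k ≥ 24, and provably not disabled if S + 5k < 24.

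| Blanks k | Attainable S | Provably not disabled | Undetermined | Provably disabled |
|---|---|---|---|---|
| 2 | 10–50 | 10–13 | 14–21 | 22–50 |
| 3 | 9–45 | none | 9–20 | 21–45 |
| 9 | 3–15 | none | 3–14 | 15 |
| 10 | 2–10 | none | 2–10 | none |

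With two blanks, only 8 of the 41 attainable sums are undetermined. Provable non-disability needs exactly two blanks, because three blanks give at least 9 + 15 = 24 as the upper bound. Provable disability is possible with up to nine blanks.

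Examples with two blanks:
- Ten items scored 4: S = 40, total 42–50, certainly disabled, yet unscored.
- Ten items scored 1: S = 10, total 12–20, certainly not disabled, yet set to 24 in (a).

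**3. Primary analysis.** Take a patient truly at or above 24 at all four visits, with one visit unscored, and require every later assessment to confirm, as in the SAP's example.

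| Unscored visit | Result |
|---|---|
| 30 days | Event kept; onset moves from day 0.10 to the 3-month onset |
| 3 months | Event kept; onset moves to the 6-month onset |
| 6 months | No event |
| 12 months | No event |

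Two looser readings would spare some cases. Accepting 30 days to 6 months as a 6-month span would rescue the 12-month row for disability present from 30 days. Skipping over a missing middle visit would rescue the 6-month row for disability that began earlier. The wording of the worked example supports neither.

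**4. Sensitivity analysis (a).** Setting a provably non-disabled visit to 24 creates a false event only if it is the 6- or 12-month visit and the other of those two is at or above 24. One case is a patient disabled only at 6 months whose 12-month form has two blanks and S = 10–13. At 30 days or 3 months it can only move an existing onset earlier.

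**5. Size.** The documents give no rate of forms with two or more blanks and no split of the expected events. Assumptions: q = 1–3% of forms per visit; 200 of the roughly 380 expected events are disability; two decisive visits.

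- Affected share: 1 − (1 − q)². For q = 0.01 this is 2.0%; for q = 0.03 it is 5.9%.
- Affected events: 200 × 0.0199 ≈ 4; 200 × 0.0591 ≈ 12.
- Provable share: 66–78% of truly disabled patients with two random blanks. This comes from a simulated 12-item ordinal scale (loadings 0.65–0.80, 10–25% at or above 24), so it too is an assumption. With three blanks it is 50–66%.
- Recoverable events: 4.0 × 0.66 ≈ 3; 11.8 × 0.78 ≈ 9.

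**6. Power.** With 1:1 allocation and two-sided α = 0.05, power = Φ(½√d × ln(1/0.75) − 1.96). For d = 380 this is 80.1%, which reproduces the SAP's 80%. For d = 377 it is 79.8%; for d = 371 it is 79.1%. The 3–9 recoverable events are therefore worth at most about one point.

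**The case against.** The strongest reply is that the SAP prespecifies a clear missing-item rule with two sensitivity analyses, and that the rule will seldom be used. Follow-up is by telephone, with a proxy if the participant is unable. Protocol section 4.6 has all fields checked, and section 4.7 monitors completeness. The only related figure is 24 of 2,570 patients (0.93%) with missing one-year data in the group's earlier trials (Protocol section 2.5), below the low end of the range assumed here. Analysis (a) is meant to be extreme. The wording of (b) leaves room to use the answered items.

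Most of this stands as a limit on size. The 0.93% is per patient and for another instrument, so it does not give the rate of part-answered WHODAS forms, but it does suggest that the rate is low. The description of (b) permits an item-level model without requiring one. An extreme scenario in (a) is reasonable for unknown status, but not for status that the answers have settled.

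Two stronger readings are tempting and are not supported:

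- **That any unscored visit costs an event.** Counting all four visits at 3% would give 1 − 0.97⁴ = 11.5%, or about 23 of 200. Only the 6- and 12-month visits can remove an event; the earlier two change its date.
- **That the treatment comparison is biased.** Patients, and the staff conducting the 1–12 month follow-ups, are blinded (Protocol section 4.3), and nothing in the documents suggests that blanks differ by arm. It is plausible that sicker or proxy-answered patients leave more blanks, but this is not documented and would not by itself differ by arm.

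**Conclusion.** The point holds as a minor one. The bounds are exact, and the loss of an event at an unscored 6- or 12-month visit follows from the SAP's own rules, read as its example reads. The false disabled label is certain only in analysis (a), possible in (b), and absent from the primary analysis.

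The size is an assumption throughout: about 4–12 events affected and 3–9 recoverable, resting on the 1–3% blank rate, the 200 disability events and the simulated provable share. A lower blank rate would shrink it in proportion. The reason to act is that the primary endpoint should not contradict recorded answers; rescuing power is not the reason.

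**What to change.** Replace the sentence on two or more missing items with a rule of this kind:

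*If k ≥ 2 items are missing and the answered items sum to S, classify the assessment as disabled if S + k ≥ 24 and as not disabled if S + 5k < 24 (possible only when k = 2). Otherwise treat it as missing.*

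- Apply it in the primary analysis and in sensitivity analysis (a), so that (a) assigns 24 only to assessments still undetermined.
- In (b), keep imputed scores between S + k and S + 5k.
- Leave the one-item rule as it is. It never contradicts the bounds for any answered sum from 11 to 55.
- For the new-onset definition, bound the change from baseline. The smallest change is the follow-up lower bound minus the baseline upper bound; the largest is the follow-up upper bound minus the baseline lower bound. Classify only if the smallest is at least 4 or the largest is below 4. Score a form with one blank by the existing rule, and let a baseline form with two or more blanks enter through its own bounds.
- Report how many forms per visit and arm had two or more blanks, and how many the bounds settled.

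The cost is one SAP sentence and a few lines of code, which can be written without treatment allocation. No new data are needed. The downside is a small departure from the stated scoring rule, confined to forms whose status is certain. The gain is also limited: with three or more blanks the rule can confirm disability but never rule it out.
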